1. Patients: Eligible patients would be identified by review of the upcoming clinic schedule of participating clinicians. We will include up to 50 English-speaking adults > 18 years old who present for evaluation of a thyroid nodule and discuss the need for thyroid biopsy. UF students and staff will be included in the study, although not targeted. We will exclude patients with hyperthyroidism, pregnant patients and those in which the nodule of interest has already been biopsied or who have received counseling by a local specialist in the year before their visit.

2. Clinicians: We will enroll clinicians that counsel patients with thyroid nodules from the endocrinology, ENT and surgery divisions at UF and from the endocrinology division at MC.

Intervention/control: We will randomize patients who need to receive counseling regarding the need for thyroid biopsy to clinicians that will use the updated conversation aid (final result of AIM1) in the intervention arm or usual counseling (without the aid) in the control arm.

In the intervention group, clinicians will conduct the encounter per standard care procedures with the addition of having access to the conversation aid for thyroid nodules prototype. The tool will be accessed online or through an available link in the Electronic Medical Record (EMR). The tool summarizes the risk for thyroid cancer, management options, prognosis of thyroid cancer and has been developed to facilitate the conversation between patients and clinicians. (See supplementary material or previously provided link.) Before clinicians use the tool, study personnel will review the conversation aid with participating clinicians and do a demonstration so that they are familiarized with the tool.

The clinician will conduct the encounter per their standard of care. As access to the tool will be available to ensure contamination does not occur the study coordinator will inform the clinician prior to entering the room that the patient is to receive standard care and that the tool is not to be accessed.

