Measurements and Outcomes. The main outcome of AIM 2 (pilot study) is to determine if conducting a larger study introducing a conversation aid for patients with thyroid nodules is feasible. This pilot study will allow us to test the performance characteristics and capabilities of study designs, measures, procedures, recruitment and operational strategies that can inform the design of a larger study. To achieve this aim we will measure the following outcomes using collected data from recordings of the medical visit, post visit survey during the day of the visit and 6-9 months for patients and at baseline and after each encounter for clinicians, and medical record review). To easy participation, surveys can be completed using printed versions in person/mail or electronic.

1. Feasibility of trial procedures. We will measure the proportion of eligible patients after review of upcoming clinical visits, enrollment and refusal reasons, ability to randomize patients and tolerability by patients and clinicians of the required assessments (time to complete assessments and obtain complete assessment at 6-9 months of follow up). This information will be obtained from adequate documentation and collection of data in pre-designed electronic forms.

2. Feasibility of using the conversation aid in clinical practice (implementation of the intervention in clinical encounters). We will evaluate the recording of clinical encounters to assess fidelity of use of the conversation aid. We will review the recordings of the control group to assess for contamination. Contamination refers to a clinician who, having used the conversation aid with a prior patient, is able to recreate elements of the conversation aid with a subsequent patient allocated to receive usual care. If there is lack of fidelity with the intervention or contamination in the control group, this would require further exploration and possible changes in the study design of a larger trial.

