C. Rate of biopsy and distribution according to guidelines recommendations. We will calculate the overall rate of biopsy at the time of visit and at 6-9 months of follow up based on chart review and patient contact. We will compare the rate of biopsy between groups according to guidelines recommendations (categorized as biopsy recommended, consider biopsy, do not perform). These recommendations are based on the size of the nodule and the risk for thyroid cancer. We will expect more variation in the group where biopsy should be considered; but will also explore the availability of the conversation aid to support conversation where thyroid biopsy should not be performed.

D. Worry/Distress. Patients that undergo surveillance for the management of low risk thyroid cancer significantly worry. Significant distress/worry in those choosing observation of a thyroid nodule might limit the implementation of conservative management. To understand the baseline and 6-month level of distress/worry, about a thyroid cancer diagnosis we will use the Impact of Event Scale (IES); a tool of 22 items scored from 0-4. We will also use four questions to assess the degree of worry based on previous studies on thyroid cancer patients (Likert score).

E. Barriers/facilitators: We will collect information regarding length of visit and satisfaction with the decision-making process, as well as fidelity to the use of the decision aid. Additional questions might be added based on the results of the in-depth assessment of feedback from patients and clinicians (AIM 1).

F. Information related to setting up the plan of care: we will collect information through video-graphic analysis in terms of discussion of the diagnostic process and next steps in the plan of care.

We will also include a single item health literacy screening, a 4 item modified subjective numeracy scale and a single item health status measure, to further characterize patients.

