In summary, patients will be identified from upcoming clinic visits and asked to participate in the study. The study description and informed consent process will be conducted on a private room. If agreeable to participate the patient and caregiver if present, will allow for video recording of their medical visit and review of their medical record to obtain information related to their past medical history and thyroid disease. After their visit, they will complete a 15-20 minute survey at the clinic or given the opportunity to mail the survey back or complete electronically. Efforts would be made to have the patient complete the visit at the day of the visit. Patients would be asked to complete a 6 month survey and given the option to complete this over the phone/mail or electronic.

The study team will contact patients by phone or email at the 6-9 month mark to follow up on the survey and have it completed. We will use phone and email recorded on the medical record and call patients to discuss how they will prefer to complete the survey. This survey could be completed on the phone or by a link that will be sent to participants that will include the an online version of the survey (Qualtrics/Redcap). If unable to talk to the patient on the phone, we will send the survey link directly.

We will attempt to contact the patients by phone/email up to three times during a 2 week period, if not response not further attempts will be completed.

Clinicians would be asked to participate at their convenience and a description of the study and the informed consent process will be conducted in a private room. A demonstration on the use of the conversation aid and a baseline survey will be completed before the first patient is enrolled. A short post visit survey will be completed after each visit.

The data from these sources (recordings of the medical visit, post visit survey during the day of the visit and 6-9 months for patients and at baseline and after each encounter for clinicians, and medical record review) will be used to evaluate the outcomes of interest.

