Contamination can result from physicians modifying their usual care practice given exposure and use of the conversation aid. Although possible, implementation of SDM in clinical practice has been a challenge suggesting clinicians do not perform these activities without the use of a conversation aid. Moreover, previous studies randomizing at the clinical encounter level have found no evidence of contamination.⁸⁶ Nonetheless, we will assess for contamination by quantifying the degree of elements of SDM noted in the control group. If contamination is noted, we will consider alternative research designs, e.g., a stepped-wedge approach by which clinicians evaluate patients as usual and start using the conversation aid at randomly selected intervals.

Statistical analysis. The distribution of study variables will be described (using frequencies for categorical variables and measures of central tendency for continuous variables) and compared using relative (relative risk) or absolute (mean differences) measures of association and their 95% CI. For the

primary aims of this study related to the feasibility of conducting a larger RCT, we will calculate the rate of successfully completing each of the identified outcomes and calculate the appropriate 95% CI. For the secondary outcomes, we will follow the intention to treat principle.

We will use standard techniques appropriate for trials, with each outcome compared between study arms using t-tests for continuous outcomes and chi-square tests for dichotomous outcomes. If there are differences in baseline characteristics found by statistical means or found to have clinical relevance between the two study groups, these will be accounted for using regression models which include an indicator for study arm.

Similarly, we anticipate evaluating (as done on previous studies) the potential clustering effect of clinicians evaluating a different number of patients. In addition, we are collecting multiple clinical variables, that can potentially affect outcomes, but in this pilot study will only serve as hypothesis generating.

Data management

Patients approached by study staff that agree to participate will be captured in the remote data capture system (REDCap). Potential eligible patients found to be ineligible or eligible but who decline participation will be captured as well. The reason for ineligibility or reason for decline will be captured along with patients' age, sex, and race/ethnicity.

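### The safeguard and the check against control patients meeting the aid stop at the index visit, while biopsy and distress are followed to 6-9 months

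*Combined protocol and SAP*

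**What the plan says.** All references are to the combined protocol and SAP.

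- **Safeguard (Intervention/control).** For a control patient, "the study coordinator will inform the clinician prior to entering the room that the patient is to receive standard care". The same sentence adds that the tool must not be opened, and it begins by conceding that the tool is not locked: "As access to the tool will be available to ensure contamination does not occur". The aid is reached online or by a link in the medical record. No patient-level block, access log or rule for later contacts is described.
- **Check (Measurements and Outcomes, item 2).** "We will review the recordings of the control group to assess for contamination". Contamination is defined there as a clinician who has used the aid before and "is able to recreate elements of the conversation aid with a subsequent patient allocated to receive usual care". The contamination paragraph just before Statistical analysis adds that "we will assess for contamination by quantifying the degree of elements of SDM noted in the control group", without naming another source or time point.
- **What is recorded (closing summary of Measurements and Outcomes).** Patient and caregiver "will allow for video recording of their medical visit and review of their medical record": one visit, in the singular.
- **Follow-up (items 3.C and 3.D).** "We will calculate the overall rate of biopsy at the time of visit and at 6-9 months of follow up", from chart review and patient contact. Distress and worry are measured at baseline and 6 months, through a survey collected in the 6-9 month window.
- **Analysis (Statistical analysis).** Secondary outcomes follow intention to treat.

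**The concern.** The protection and the measurement share one time point, the index encounter, but two outcomes run months beyond it. The alternative to biopsy is surveillance by repeated ultrasound (Abstract), so a further conversation about the nodule before 6-9 months is plausible. Enrolment is planned over 18 months (Sample size), so controls enrolled early would be followed while participating clinicians are still using the aid with other patients. The plan already treats counselling outside the index visit as relevant: it excludes patients counselled by a local specialist in the preceding year. It has no counterpart after the visit.

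Two things are at stake. First, if the aid works and is used later with a control patient, that patient's later biopsy status and distress move toward the intervention arm. Second, contamination is itself a feasibility outcome. The plan says contamination could change the design of the larger trial and names a stepped-wedge alternative. A clean result from one visit might be taken as support for randomising individual patients with a 6-9 month biopsy endpoint, although contamination over that period was never observed. If later use is not recorded at the time, it may not be recoverable afterwards.

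**Working it through.** **1. Coverage by time point**

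| | Index visit | After it, to 6-9 months |
|---|---|---|
| Instruction not to use the aid with controls | yes | not stated |
| Aid reachable by clinicians | yes | no end or restriction stated |
| Recording reviewed for contamination | yes | none planned |
| Biopsy rate | yes | yes |
| Distress and worry | yes (baseline) | yes |
| Knowledge, risk estimate, decisional conflict, OPTION | yes (visit or post-visit survey) | not the source |

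The gap concerns the later biopsy rate and later distress only. The contamination definition also concerns carry-over from one patient to a subsequent one. The same control patient meeting the aid itself at a later contact is not named in it.

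**2. The plan's own figure**

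Inputs (Sample size): control proportion 0.60 for adequate biopsy selection, detectable difference 0.27, 41 per arm, alpha 0.05 (taken as two-sided), 80% power. With pooled variance and no continuity correction:

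power = Φ{[d√n − 1.96√(2p̄(1−p̄))] / √(p1(1−p1) + p2(1−p2))}

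With p1 = 0.60, p2 = 0.87, p̄ = 0.735, n = 41:

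- d√n = 0.27 × 6.403 = 1.729
- 1.96 × √(2 × 0.735 × 0.265) = 1.223
- denominator = √(0.2400 + 0.1131) = 0.594
- power = Φ(0.506/0.594) = Φ(0.851) = 80.3%

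The stated figure reproduces.

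**3. What later exposure would do, if it occurred**

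Let s be the share of controls exposed later and e the fraction of the full effect that late exposure carries, and put c = s × e. The control proportion becomes 0.60 + 0.27c and the difference 0.27(1 − c), with 0.87 held in the intervention arm. The documents give neither s nor e, so both are assumptions.

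| c | Control proportion | Difference (points) | Power, 41 per arm | Per arm for 80% |
|---|---|---|---|---|
| 0 | 0.600 | 27.0 | 80.3% | 41 |
| 0.05 | 0.6135 | 25.65 | 76.6% | 45 |
| 0.10 | 0.627 | 24.3 | 72.6% | 49 |
| 0.20 | 0.654 | 21.6 | 63.6% | 60 |
| 0.30 | 0.681 | 18.9 | 53.7% | 76 |

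The row c = 0.10 is 10% of controls exposed at full effect, or 20% at half effect. The row c = 0.05 is 10% exposed at half effect; with 45 per arm (90 enrolled), power there is 80.4%.

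**4. Limits of the illustration**

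The Sample size section does not say when adequate selection is judged. If it is judged at the visit, none of the reductions applies to it. The 27 points is a detectable difference, not an expected effect. No corresponding figures exist for distress. The table shows direction and sensitivity, not a predicted loss.

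**The case against.** The strongest reply is that the route of exposure is undocumented. The plan schedules no second study visit, gives no ultrasound interval and does not say that patients return for counselling before 6-9 months, so the exposed share could be close to zero. This stands, and it is why no size can be assigned.

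Late exposure is also unlikely to carry the full effect. It cannot undo a biopsy already done, and a biopsy recorded by 6-9 months may simply carry out the decision made at the index visit. This stands too: the full-effect rows are upper-end cases.

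A biopsy rate at the visit, before any later exposure, is already planned. The main outcome is feasibility, and the plan itself calls the sample too small to settle efficacy. Under intention to treat, later routine care can be regarded as part of the comparison. These points lower the weight of the concern but do not answer it, because contamination is one of the feasibility findings and would be reported from the index visit alone.

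It can also be said that control is defined as usual counselling without the aid and that clinicians know the allocation. That does not clearly reach later visits or other clinicians, and nothing would show whether it had been respected.

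A reader might infer that the 6-9 month comparisons will be biased, or that the trial will lose the power tabulated above. The documents do not support either reading: they show an unguarded and unmeasured route, not that anyone takes it.

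**Conclusion.** The gap is real and modest. The instruction and the contamination check cover the index visit only, the aid stays reachable, and nothing planned would record its later use with a control patient. Such use would move the 6-9 month biopsy and distress comparisons toward no difference, assuming the aid has an effect and later use acts in the same direction as use at the index visit. The reported contamination rate would not reveal it.

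The size is unknown. It runs from nothing, if no control patient meets the aid later, to the illustrative losses above. The visit-time comparisons stand as planned. The gap does not undermine the pilot's feasibility conclusions in general. It limits one of them: whether randomising individual patients can support a follow-up endpoint in the larger trial.

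**What to change.** 1. **Intervention/control.** State that the instruction not to access the aid for a control patient applies to participating clinicians at all contacts about the study nodule until the 6-9 month assessment, and place a flag in the patient record.
2. **6-9 month chart review.** For both arms, record any later visit about the nodule and any use of the aid, with dates. Take this from chart notes, access to the record link where available, or the treating clinician. Do not name the aid in the patient survey: patients are kept blind to the research question (Enrollment, randomization and blinding), and that survey also measures worry.
3. **Measurements and Outcomes, item 2.** Report the result as a second, post-visit contamination rate, with the number of controls who had any later visit beside it.
4. **Analysis.** Interpret the 6-9 month biopsy comparison beside the visit-time rate, by intention to treat. Do not exclude exposed controls: patients who return for further discussion are likely to differ on the biopsy outcome, so removing them would be a selection made after randomisation.

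The cost is some protocol wording, a record flag and a few fields in a chart review already planned. Clinicians must respect the allocation for several months instead of one visit. Charts may not capture every use of the aid, so the rate should be presented as a lower bound.

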Enrollment, randomization and blinding: Eligible patients will be allocated using a random sequence generated by the study statistician at UF. Study coordinators at both sites will approach eligible patients at the time of their visit and invite them to participate. Once the patient is enrolled, the coordinator will obtain their allocation using an online tool, allowing for allocation concealment. Clinicians will be aware of the arm to which the patient has been randomized. Patients will be blinded to the research question, as informed consent documents will only inform them of the goal of testing different communication approaches. Data analysts, statisticians, video reviewers, will not be blinded to group allocation given the pilot nature of this project.

Consent.

1) Patients. Patients would be invited to participate once they have been roomed and are waiting to see their clinician. The informed consent process will take place in a private room. We will obtain written informed consent, consent for video/audio recording and authorization for medical chart review to obtain information related to their medical history and thyroid nodule features. Study participation also includes completion of a post visit survey and a 6 month follow up survey (in person/mail/electronic version).

2) Clinicians. Eligible clinicians are those who counsel patients with thyroid nodules. We will approach eligible clinicians at their convenience to discuss the goals of the study and their potential participation. We will obtain written informed consent and consent for audio/video recording. Study participation also includes completion of a baseline survey and post visit short survey (in person/electronic).

3) Guest. If an eligible patient has a caregiver/guest with them we will seek the consent for participation given that their participation during the medical visit would be recorded. If a guest does not want to participate, the patient would not be included in the study as we don't want to disrupt their visit dynamic. Informed consent and consent for audio/video recording will be obtained.

4) Other. Commonly, clinicians would work with scribes, students, and other ancillary staff. We will obtain consent for audio/video recording during the medical visit.

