3. Empirical evidence of the study parameters for the outcomes of interest. Preliminary information regarding outcomes in pilot studies is at risk for bias due to imprecision associated with small samples sizes; a future randomized clinical trial would be powered using clinically significant differences. The main goal of this study is to assess the feasibility of assessing the effect of this novel conversation aid to increase the likelihood of completing a subsequent larger efficacy trial. However, obtaining information about study parameters would be helpful.

We will measure these outcomes by direct observation of recorded clinical visits and post-visit questionnaires given to patients and their clinicians.

A. Quality of SDM. The quality of decision-making is multidimensional. To measure the quality of SDM we will measure: 1) Knowledge transfer: assessed using a 13-item questionnaire that would include 10 questions related to the content of the conversation aid and three questions not contained in the conversation aid. We would expect similar performance between the groups in the questions that are not included in the conversation aid. 2) Risk communication: assessed by asking patients to estimate their risk for thyroid cancer, as ____ out of 100 people just like you. 3) Satisfaction of patients and

clinicians with the amount of information shared and recommendation for the use SDM to others, assessed with a single item (Likert format). 4) Patient satisfaction with their decision assessed using the Decisional Conflict Scale (DCS), a 16-item, extensively validated, and commonly used scale.

B. Processes of SDM. We will explore:1) the degree to which clinicians involved patients in the medical decision process, by evaluating the clinical visit recordings using the OPTION score. This is a 12-item scale that is based on review of clinical encounters with each item receiving a score of 0-4. It has been validated and is used extensively in SDM trials.

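### Video reviewers are left unblinded only because the study is a pilot, although they make the OPTION, fidelity and contamination ratings; withholding the allocation is cheap and would reduce expectation bias

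*Combined protocol and SAP*

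**What the plan says.** The rule is in the section on enrollment, randomization and blinding: "Data analysts, statisticians, video reviewers, will not be blinded to group allocation given the pilot nature of this project". No other reason is offered there or elsewhere.

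Three outputs come from the recordings:

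- **OPTION** (Measurements and Outcomes, 3.B). Patient involvement is rated "by evaluating the clinical visit recordings using the OPTION score". On the instrument, the protocol says: "This is a 12-item scale that is based on review of clinical encounters with each item receiving a score of 0-4". Under Statistical analysis, continuous outcomes are compared between arms by t-test.
- **Fidelity** (Measurements and Outcomes, item 2): "We will evaluate the recording of clinical encounters to assess fidelity of use of the conversation aid".
- **Contamination** (same item): "We will review the recordings of the control group to assess for contamination". The paragraph on contamination before Statistical analysis adds that "we will assess for contamination by quantifying the degree of elements of SDM noted in the control group".

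Item 2 says that poor fidelity or contamination may lead to a different design for the larger trial. The contamination paragraph names a stepped-wedge approach as one alternative.

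That paragraph also records a prior expectation. It allows that contamination could happen, but describes past difficulty in implementing shared decision-making as "suggesting clinicians do not perform these activities without the use of a conversation aid", and cites earlier encounter-randomised studies that found no contamination. It still commits to checking for it.

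The documents mention no masked or independent rater, duplicate scoring, inter-rater agreement or rater calibration.

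**The concern.** OPTION items are graded judgements about a conversation. A rater who knows the arm, and knows the hypothesis that the aid supports shared decision-making, can score the same behaviour differently in the two arms. That adds a spurious component to the between-arm difference, and no analysis of the scores can separate it from a real effect.

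Fidelity and contamination raise a different problem. Contamination is assessed in control recordings, and fidelity concerns use of the aid where it was assigned. Knowledge of the arm can therefore distort each rate, but it does not create an arm difference in them. These two ratings belong to the feasibility aim, and a wrong contamination rate could lead the larger trial to keep or abandon encounter-level randomisation for a poor reason.

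Pilot status does not explain the rule. Nothing about a pilot prevents withholding the allocation from the people who score recordings, and a stated purpose of this pilot is to try out measures and procedures for the later trial.

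**Working it through.** **Inputs from the documents.** There are 41 patients per arm and alpha is 0.05 (Sample size). OPTION has 12 items scored 0-4 (3.B). Continuous outcomes are compared by t-test (Statistical analysis). The sidedness of the test is not stated; two-sided is used here because it reproduces the plan's figures.

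**Inputs that are assumed.** The documents give neither an OPTION SD nor any size of rater bias. Both are assumed: a uniform lenience of 0.25 or 0.1 points on every item in every aid-arm recording, and an SD of 10, 15 or 20 on a 0-100 scale.

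**Step 1: the plan's own figures.** With n = [1.96 × √(2p̄q̄) + 0.842 × √(p₁q₁ + p₂q₂)]² / (p₂ − p₁)²:

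- 45% v 75%: (1.358 + 0.555)² / 0.09 = 40.7, so 41 per arm.
- 60% v 87%: (1.223 + 0.500)² / 0.0729 = 40.7, so 41 per arm.
- 95% interval for 15% of 41: 0.15 ± 1.96 × √(0.15 × 0.85 / 41) = 4.1% to 25.9%, against the stated 4% to 26%.

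All reproduce. None concerns OPTION, fidelity or contamination, for which the plan states no figure.

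**Step 2: size of the assumed shift.** The OPTION maximum is 12 × 4 = 48.

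- 0.25 × 12 = 3 points; 3/48 = 6.25 on a 0-100 scale.
- 0.1 × 12 = 1.2 points; 1.2/48 = 2.5 on a 0-100 scale.

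**Step 3: chance of p<0.05 with no true effect.** The standard error of the difference is SD × √(2/41). The rejection rate is that of a two-sided two-sample t-test with 80 degrees of freedom and noncentrality shift/SE.

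| SD (assumed) | SE | Shift 6.25: shift/SE | p<0.05 | Shift 2.5: shift/SE | p<0.05 |
|---|---|---|---|---|---|
| 10 | 2.21 | 2.83 | 80% | 1.13 | 20% |
| 15 | 3.31 | 1.89 | 46% | 0.75 | 12% |
| 20 | 4.42 | 1.42 | 29% | 0.57 | 9% |

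The nominal rate is 5%.

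**Step 4: relation to what the pilot can detect.** At 41 per arm and 80% power, the detectable standardised difference is 0.63 SD. The 6.25-point shift is 0.63, 0.42 or 0.31 SD for an SD of 10, 15 or 20; the 2.5-point shift is 0.25, 0.17 or 0.13 SD.

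**Step 5: fidelity and contamination.** No arithmetic applies. The documents give no rate, threshold or scoring rule from which a bias could be sized.

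**The case against.** The strongest reply is that masking would often fail. Where the aid is opened on screen or talked through, the reviewer will recognise the arm, and if it is usually opened, its absence hints at control. This stands. Masking can help only in recordings where the arm is not evident: aid-arm visits in which the tool was not used, control visits that resemble them, and some audio-only recordings (offered under Possible Discomforts and Risks). Their number is unknown. The protocol does not itself give impracticability as its reason, and partial masking is still better than a rule that rules out any.

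Second, the study is a pilot. The Sample size section says it cannot settle efficacy, item 3 says the future trial would be powered on clinically significant differences, and OPTION is exploratory. This also stands, and it limits the harm. A reader might take the rejection rates above as evidence that the pilot will produce a false-positive efficacy result. The documents do not support that: no decision depends on the OPTION p-value, and both the lenience and the SD are assumptions.

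Third, a reader might infer that the bias must favour the tool and the current design. The expectation written into the contamination paragraph makes this plausible but does not show it. Reviewers sent to control recordings specifically to look for contamination could search harder as easily as less hard, and the same paragraph plans a response if contamination is found.

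**Conclusion.** The concern holds as a minor to moderate weakness. A stated rule leaves the raters of subjective outcomes unblinded, the only reason given does not prevent masking, and no other safeguard is described. The between-arm argument applies to OPTION alone. For fidelity and contamination the risk is a distorted single-arm rate of unknown direction.

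The 9% to 80% range in the table shows how sensitive a comparison of this size is to modest rater lenience. It is not an estimate of the bias in this trial, nor of how much partial masking would remove. What is at stake is the preliminary OPTION estimate and the fidelity and contamination findings that inform the larger trial, not a confirmatory test.

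A reader might also infer from the blinding sentence that reviewers are actively given each patient's allocation. The text says only that they are not blinded.

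**What to change.** 1. Remove video reviewers from the list of unblinded roles.
2. Have a coordinator who does not rate supply recordings from both arms under study number, in random order and without the allocation.
3. Score OPTION first. Then apply one aid-element checklist to every recording, to be read after unmasking as fidelity in the aid arm and contamination in the control arm.
4. Have the reviewer note for each recording whether the arm was recognised, and report masking as partial. This also tells the larger trial how far masking can be achieved.

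The cost is some file handling, a checklist on every recording, keeping reviewers away from allocation data that other study personnel hold, and a paragraph of protocol text. No extra patients or readers are needed. Masking will remain incomplete wherever the aid is seen or heard.
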